9.2.2 Drug Induced Liver Injury (DILI)

Total bilirubin level should be checked for any subject with increased ALT or AST levels \geq three times the upper normal limits (ULN) or baseline.

- Reporting all DILI as SAE to the FDA based on Hy's Law:
 - AST or ALT \geq 3 x ULN or baseline and
 - T_Bili \geq 2 x ULN or baseline

A separate incidence table will be provided for DILI cases, and the corresponding listing will be provided for Safety Sample during the double-blind treatment period and the single-blind placebo run-in period.

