5.6 Potential Serious Hepatotoxicity

For a subject who experiences an elevation in aspartate aminotransferase (AST) or alanine aminotransferase (ALT) that is ≥ 3 times the upper limit of normal (ULN), a total bilirubin level should also be evaluated. If the total bilirubin is ≥ 2 times the ULN, complete an IRE form with all values listed and also report as an AE on the eCRF.

Protocol 405-201-00014

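### SAP 9.2.2 defines DILI by multiples of ULN or baseline, Protocol 5.6 by ULN alone; read literally, the SAP can count a case whose values all stay in the normal range

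*SAP*

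**What the plan says.** SAP 9.2.2 first asks for a bilirubin check when ALT or AST is at least "three times the upper normal limits (ULN) or baseline". Its case rule has two limbs joined by *and*. The transaminase limb is AST or ALT at or above "3 x ULN or baseline and" the bilirubin limb is total bilirubin at or above "2 x ULN or baseline". The rule is introduced by the line "Reporting all DILI as SAE to the FDA based on Hy's Law". On output, the SAP says "A separate incidence table will be provided for DILI cases", with a listing, for both the double-blind and the run-in periods. In the SAP's table list (Section 13) these are CT-10.4.1 and 10.4.2 (incidence) and CT-10.5.1 and 10.5.2 (listings).

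Protocol 5.6 covers the same situation with ULN as the only reference. When AST or ALT reaches "3 times the upper limit of normal (ULN), a total bilirubin level should also be evaluated". If bilirubin is then at least 2 "times the ULN, complete an IRE form with all values listed and also report as an AE on the eCRF".

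SAP Appendix 2, the criteria for potentially clinically relevant laboratory values, flags AST and ALT at 3 x ULN and total bilirubin at 2.0 mg/dL. It has no baseline alternative for any of the three.

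**The concern.** The two documents define what should be the same liver event in different ways, and the SAP definition drives the safety tables. Adding baseline as an alternative reference lets a small absolute rise from a low-normal starting value satisfy a limb. If both limbs can be met that way, a subject could appear in the DILI count without any abnormal result. That subject would meet no Protocol 5.6 criterion and would have no AST, ALT or bilirubin value flagged under Appendix 2.

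This matters because counts of such cases are usually small, so one or two extra subjects in an arm can change how the row is read. The table would also fail to reconcile with the events that sites were asked to report.

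**Working it through.** The plan states no figure on this point, so there is nothing to reproduce. The check is threshold arithmetic on the two rules.

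**Inputs.** SAP 9.2.2: multiples 3 (AST/ALT) and 2 (bilirubin), applied to ULN or baseline. Protocol 5.6: multiples 3 and 2, applied to ULN. The documents give no ULN values, so the general result is in units of ULN.

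**Formula.** Let b = baseline / ULN. Read literally, *or* means that meeting either reference is enough, so the lower threshold governs:

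- SAP, AST/ALT: min(3, 3b) x ULN. Protocol: 3 x ULN.
- SAP, bilirubin: min(2, 2b) x ULN. Protocol: 2 x ULN.

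| b | AST/ALT, SAP (x ULN) | AST/ALT, Protocol | Bilirubin, SAP (x ULN) | Bilirubin, Protocol |
|---|---|---|---|---|
| 0.25 | 0.75 | 3 | 0.50 | 2 |
| 0.30 | 0.90 | 3 | 0.60 | 2 |
| 0.40 | 1.20 | 3 | 0.80 | 2 |
| 0.50 | 1.50 | 3 | 1.00 | 2 |
| 0.75 | 2.25 | 3 | 1.50 | 2 |
| 1.00 | 3.00 | 3 | 2.00 | 2 |
| 1.50 | 3.00 | 3 | 2.00 | 2 |

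**Results for any ULN.**

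1. For b below 1 the SAP threshold is lower than the Protocol's. For b at or above 1 they coincide. On the literal reading, the baseline alternative therefore acts only on subjects whose baseline is below ULN.
2. The AST/ALT threshold is inside the normal range when 3b < 1, that is, baseline below ULN/3. The bilirubin threshold is inside it when 2b < 1, that is, baseline below ULN/2.
3. Both limbs are required, so an all-normal DILI case needs both conditions in the same subject.
4. The SAP threshold never exceeds the Protocol's, so every subject meeting 3 x ULN and 2 x ULN is still counted.

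**Illustration over a range of assumed ULNs.**

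- ALT, ULN 35 U/L: 35/3 = 11.7. A baseline of 10 is flagged at 30 (Protocol: 105).
- ALT, ULN 40 U/L: 40/3 = 13.3. A baseline of 10 is flagged at 30 (Protocol: 120).
- ALT, ULN 55 U/L: 55/3 = 18.3. A baseline of 15 is flagged at 45 (Protocol: 165).
- Bilirubin, ULN 1.0 mg/dL: 1.0/2 = 0.5. A baseline of 0.4 is flagged at 0.8 (Protocol: 2.0).
- Bilirubin, ULN 1.2 mg/dL: 1.2/2 = 0.6. A baseline of 0.4 is flagged at 0.8 (Protocol: 2.4).

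With ULNs of 40 U/L and 1.2 mg/dL, ALT rising from 10 to 30 and bilirubin from 0.4 to 0.8 meets both SAP limbs. All four values are normal, and none reaches the Appendix 2 criteria (120 U/L and 2.0 mg/dL).

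**Effect of the baseline term.** Without it the thresholds are 3 x ULN and 2 x ULN whatever the baseline, and no normal-range value can be flagged.

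**The case against.** The strongest reply is that the baseline reference was meant only for subjects who enter with raised values. SAP 9.2.2 does speak of increased ALT or AST, and exclusion criterion 18 bars only AST or ALT above 2 x ULN, so such subjects can be enrolled. But neither document states this limit, and an increased value need not be above ULN. Nor would that reading remove the mismatch. If a raised baseline replaces ULN, a subject starting at 1.5 x ULN would need 3 x 1.5 = 4.5 x ULN under the SAP against 3 x ULN under the Protocol. The disagreement would then run the other way. Two programmers could build different tables from the same sentence.

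Three stronger inferences are tempting, and the documents do not support them.

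- *The tables will report false Hy's Law cases.* The listed titles of CT-10.4 and CT-10.5 refer to laboratory abnormalities potentially related to liver injury, not to DILI or Hy's Law, and the row labels are not shown. The DILI and Hy's Law labels stand in the text of SAP 9.2.2. Neither document gives another definition of Hy's Law against which to call the SAP version wrong.
- *Real cases are lost or hidden.* On the literal reading none is lost. The listings show the flagged subjects, and Appendix 2 gives ULN-based AST and ALT counts, although by single test and not jointly.
- *The reporting instructions contradict each other.* Protocol 5.3 and 5.6 tell the site what to send to the sponsor; the SAP line concerns a report to the FDA. Both can be done. What stands is that the SAP does not say how its line relates to the Protocol's IRE and AE route, and a case met only through the baseline term would trigger no site report under Protocol 5.6.

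**Conclusion.** The point holds as a mismatch of definitions. SAP 9.2.2 as written is wider than Protocol 5.6 for every subject with a baseline below ULN. It can count an all-normal subject as DILI when the AST or ALT baseline is below ULN/3 and the bilirubin baseline is below ULN/2. This follows for any ULN; the numerical examples rest on assumed ULNs. It also rests on reading *or* literally, which no other text overrides.

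The error can go only one way on that reading: the DILI count may exceed the events that Protocol 5.6 defines, and it cannot fall short of them. How often is unknown. Both limbs must be met, the documents give no distribution of liver tests, and all-normal cases may be few. The effect is confined to the liver tables and listings; the efficacy analyses are untouched. It still deserves correction, because a stated counting rule yields a number that does not mean what its label says.

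**What to change.** Reconcile SAP 9.2.2 with Protocol 5.6 so that one written criterion defines the DILI/Hy's Law row in CT-10.4.1 and 10.4.2 and the matching listings. Which clinical threshold to use is for the sponsor's safety function; this review takes no position on it.

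If baseline-multiple flags are kept, state exactly when the baseline reference applies and show those flags on separate rows, not labelled DILI or Hy's Law.

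For the line "Reporting all DILI as SAE to the FDA based on" Hy's Law, either say how it relates to the IRE form and AE entry in Protocol 5.6 or remove it from the SAP.

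The cost is a few sentences of SAP text and some table-shell rows. No new data are needed, since AST, ALT and total bilirubin are already in the routine chemistry panel.

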9.2.3 Clinical Laboratory Tests in the Single-blind Placebo Run-in Period

Potentially clinically relevant laboratory measurement test results in the Single-blind Placebo Run-in Period will be summarized for the Safety Sample by treatment group and overall as well as listed by subject and by laboratory test.

9.3 Vital Signs

Summary statistics for vital signs will be provided. For the double-blind treatment period vital signs, change from baseline for the double-blind treatment period will be summarized for the Safety Sample by treatment group. Potentially clinically relevant results in vital signs will also be summarized. Similar summaries will be provided for the Safety Sample during the Single-blind Placebo Run-in Period.

9.3.1 Vital Signs in the Double-Blind Treatment Period

Potentially clinically relevant vital signs measurements identified in the double-blind treatment period for the Safety Sample will be summarized by treatment group. Criteria for

SAP 405-201-00014

identifying vital signs of potential clinical relevance are provided in [Appendix 1](#). All potentially clinically relevant events or changes will be listed and included in summary tables.

9.3.2 Vital Signs in the Single-blind Placebo Run-in Period

Potentially clinically relevant vital signs measurements identified in the Single-blind Placebo Run-in Period for the Safety Sample will be summarized by treatment group.

9.4 Electrocardiogram (ECG) Data

Summary statistics and incidence of potentially clinically relevant changes will be provided for ECG parameters.

For the analysis of QT and QTc, data from three consecutive complexes (representing three consecutive heart beats) will be measured to determine average values. The following QT corrections will be used for reporting purposes in the clinical study report:

- 1) QTcB is the length of the QT interval corrected for heart rate by the Bazett formula:
 $QTcB = QT / (RR)^{0.5}$ and
- 2) QTcF is the length of the QT interval corrected for heart rate by the Fridericia formula:
 $QTcF = QT / (RR)^{0.33}$
- 3) QTcN is the length of the QT interval corrected for heart rate by the FDA Neuropharm Division formula: $QTcN = QT / (RR)^{0.37}$

9.4.1 ECG Data in the Double-Blind Treatment Period

Potentially clinically relevant changes in the 12-lead ECG identified in the double-blind treatment period for the Safety Sample will be listed and summarized by treatment group. Criteria for identifying ECG measurements of potential clinical relevance are provided in [Appendix 3](#).

Categorical changes in ECG parameters during the double-blind treatment period will be summarized based on the following criteria:

Categorical Change Criteria in QT/QTc Parameters		
Classification	Category	Criteria
QT	New Onset (> 450 Msec)	New onset (>450 msec) in QT means a subject who attains a value > 450 msec during treatment period but not at baseline.
QTc *	New Onset (> 450 Msec)	New onset (> 450 msec) in QTc means a subject who attains a value > 450 msec during treatment period but not at baseline.

SAP 405-201-00014

Categorical Change Criteria in QT/QTc Parameters		
Classification	Category	Criteria
	New Onset (> 450 Msec) And > 10% Increase	New onset (> 450 msec) and > 10% increase in QTc means a subject who attains a value > 450 msec and > 10% increase during treatment period but not at baseline
	New Onset (> 500 Msec)	New onset (> 500 msec) in QTc means a subject who attains a value > 500 msec during treatment period but not at baseline.
	Increase 30 - 60 Msec	Increase from baseline value > 30 and ≤ 60 msec in QTc
	Increase > 60 Msec	Increase from baseline value > 60 msec in QTc

* QTc categorical change criteria apply to QTcB, QTcF and QTcN.

9.4.2 ECG Data in the Single-blind Placebo Run-in Period

Potentially clinically relevant changes in the 12-lead ECG identified in the Single-blind Placebo Run-in Period for the Safety Sample will be listed and summarized by treatment group.

9.5 Physical Examinations

By-patient listings will be provided for physical examination.

9.5.1 Body Weight, Waist Circumference and Body Mass Index (BMI)

Analyses of body weight, waist circumference and BMI will be performed for the Safety Sample. The mean change from baseline of the double-blind treatment period to Day 42 (OC) and last visit in the double-blind treatment period in body weight will be tabulated and analyzed using ANCOVA. The ANCOVA models for both the OC and last visit analyses will include the baseline of the double-blind treatment period body weight and the treatment group.

Percentages of patients showing significant weight gain ($\geq 7\%$ increase in weight), as well as percentages of patients showing significant weight loss ($\geq 7\%$ decrease in weight) baseline of the double-blind treatment period to Day 42 (OC and LOCF) will be analyzed using Cochran-Mantel-Haenszel (CMH) General Association Test.

Body mass index is defined as weight in kilograms divided by the square of height in meters.

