1.3 Known and Potential Risks and Benefits

Based on the IB, data from the completed phase 1 and 2 trials indicate that centanafadine is safe and well-tolerated in healthy adult subjects and adult subjects with ADHD. Data from the completed phase 2 trials demonstrate that centanafadine is effective in treating symptoms of ADHD; based on the positive effect of centanafadine SR on the primary efficacy measure, the adult ADHD-RS-IV. Preliminary data suggest centanafadine may also confer an improved safety profile and a lower potential for abuse compared to currently approved Schedule II stimulant treatments for ADHD. The abuse potential for centanafadine is continuing to be evaluated.

Seven clinical trials in 260 healthy adult subjects and adult subjects with ADHD have been conducted with centanafadine. A total of 140 healthy adult subjects received centanafadine in 5 phase 1 trials and 120 adult subjects with ADHD received centanafadine in 2 phase 2 trials. The most common AEs reported in trials with centanafadine SR at TDDs ranging from 25 to 800 mg were gastrointestinal (nausea, diarrhea, and dry mouth), metabolism/nutrition-related (decreased appetite), and nervous system disorders (headache, dizziness, and insomnia). In general, these AEs were mild and resolved. To date, 1 serious AE (SAE) (ischemic cardiovascular accident) occurred in

Protocol 405-201-00014

a subject with ADHD (initial dosage of centanafadine SR 100 mg, titrated to 500 mg) 6 days after completing treatment, but it was not considered related to centanafadine treatment.

Based on the outcome of the phase 2 trials, treatment with centanafadine may be associated with increases in blood pressure, heart rate and orthostatic blood pressure changes. Increases in blood pressure and heart rate were usually modest and asymptomatic; however, hypertension, tachycardia, and orthostasis have occurred. During clinical trials, heart rate and blood pressure will be measured prior to initiation of therapy, and periodically while on therapy. Subjects will also be monitored for tachycardia or hypertension. Centanafadine should be used with caution in subjects with hypertension, tachycardia, or cerebrovascular disease or cardiovascular disease (eg, known serious structural cardiac abnormalities, cardiomyopathy, serious heart rhythm abnormalities, or other serious cardiac problems that may place a subject at increased vulnerability to noradrenergic effects).

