3.7 Trial Procedures

The time from enrollment of the first subject to the last subject's last trial visit will be approximately 12 months. Individual participation for subjects who complete the trial will be approximately 12 weeks, consisting of a 28-day screening and washout period, a 1-week single-blind placebo run-in period, a baseline day, a 6-week double-blind treatment period, and a 7-day follow-up period (follow-up telephone calls at 1, 3, and 5 days after the last dose of IMP, and in-clinic visits 2 and 7 days after the last dose of IMP). For subjects who terminate early, decide to not enroll in Trial 405-201-00015, or who are not eligible to enroll in Trial 405-201-00015, they will be required to participate in the 7-day follow-up period as well as participate in an additional follow-up telephone call 10 days after the last dose of IMP.

When Trial 405-201-00014 reaches its conclusion, all subjects participating in the trial, regardless of trial period, may be eligible to enroll into Trial 405-201-00015, which is a 12-month, observational, open-label trial ([Section 3.1](#)). All subjects will be required to comply with the appropriate follow-up procedures described in [Section 3.7.1.5](#) and [Section 3.7.1.6](#).

Trial assessment time points are summarized in [Table 3.7-1](#) and [Table 3.7-2](#).

Protocol 405-201-00014

Period	Screening ^a	PBO Run-in ^b	Double-blind Treatment							NOTES
			Baseline Day -1	Day 7 +1 Day	Day 14 ±2 Days	Day 21 ±2 Days	Day 28 ±2 Days	Day 35 ±2 Days	Day 42/ET ±2 Days	
Visit	1	2	3	4	5	6	7	8	9	
ENTRANCE/HISTORY										
Informed consent	X									Section 3.4.1
Inclusion/exclusion criteria	X	X	X							Section 3.4
Demography	X									
Concomitant medication(s)	X	X	X	X	X	X	X	X	X	
Medical history	X	X	X							
ACDS	X									
Identification of comorbidities using MINI	X									
Psychiatric evaluation	X									
HIV/HBsAg/anti-HCV	X									Section 3.7.5.2
Randomization			X							Section 3.6.1
Urine pregnancy test	X	X	X	X	X	X	X	X	X	Section 3.7.5.2 Section 5.7
EFFICACY										
AISRS	X	X	X	X	X	X	X	X	X	Section 3.7.2.1
CGI-S			X	X	X	X	X	X	X	Section 3.7.2.2
CGI Change from Baseline				X	X	X	X	X	X	Section 3.7.2.3
SAFETY										
Adverse events	X	X	X	X	X	X	X	X	X	Section 5.2
Physical examination	X					X			X	Section 3.7.5.3.1
Vital signs	X	X	X	X	X	X	X	X	X	Section 3.7.5.3.2
12-lead ECG	X	X	X	X	X		X		X	Section 3.7.5.4
Clinical laboratory tests	X	X	X		X				X	Section 3.7.5.2
SMWQ								X	X	Section 3.7.5.5.1

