3.7.5.3 Physical Examination and Vital Signs

3.7.5.3.1 Physical Examination

A complete physical examination will be performed at screening, and a targeted physical examination to address any new concerns will be performed at all other visits indicated in the Schedule of Assessments ([Table 3.7-1](#)). A complete physical examination will include height (screening only), weight, waist circumference, and calculation of body mass index (BMI) (screening and Day 42/ET only); and assessment of the head, eyes, ears, nose, throat, thorax, abdomen, urogenital, skin and mucosae, neurological, and extremities. Examinations with abnormal results that are deemed clinically significant should be repeated to ensure reproducibility of the abnormality. Any abnormalities considered by the investigator to be clinically significant are to be recorded as AEs on the AE eCRF.

Protocol 405-201-00014

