3.7.5.3.2 Vital Signs

Vital signs including systolic blood pressure and diastolic blood pressure, heart rate, respiratory rate, and body temperature will be measured at the time points described in the Schedule of Assessments ([Table 3.7-1](#) and [Table 3.7-2](#)). Blood pressure and heart rate measurements will be made in the supine and standing positions after the subject has been in each position for at least 3 minutes. The supine measurements will be performed first followed by the standing measurements. Temperature and respiratory rate will be taken with the subject in the supine position.

Subjects should be monitored for potentially clinically significant vital signs values ([Appendix 3](#)). Abnormal results that are deemed clinically significant should be repeated to ensure reproducibility of the abnormality. Any abnormalities considered by the investigator to be clinically significant are to be recorded as AEs on the AE eCRF ([Section 5.2](#)).

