Appendix 1 Criteria for Identifying Vital Signs of Potential Clinical Relevance

Variable	Criterion Value ^a	Change Relative to Baseline ^a
Heart Rate ^b	> 100 bpm < 50 bpm	≥ 10 bpm increase ≥ 10 bpm decrease
Systolic Blood Pressure ^b	≥ 140 mmHg < 90 mmHg	≥ 20 mmHg increase ≥ 20 mmHg decrease
Diastolic Blood Pressure ^b	≥ 90 mmHg < 60 mmHg	≥ 10 mmHg increase ≥ 10 mmHg decrease
Orthostatic Hypotension	≥ 30 mmHg decrease in systolic blood pressure or a ≥ 20 mmHg in diastolic blood pressure after at least 3 minutes of standing compared to the previous supine blood pressure.	Not Applicable (baseline status not considered)
Orthostatic Tachycardia	≥ 25 bpm increase in heart rate from supine to standing	Not Applicable (baseline status not considered)
Weight	-	≥ 7% increase ≥ 7% decrease

^a In order to be identified as potentially clinically relevant, an on-treatment value must meet the “Criterion Value” and also represent a change from the subject’s baseline value of at least the magnitude shown in the “Change Relative to Baseline” column.

^b As defined in “Supplementary Suggestions for Preparing an Integrated Summary of Safety Information in an Original NDA Submission and for Organizing Information in Periodic Safety Updates,” FDA Division of Neuropharmacological Drug Products draft (2/27/87).

SAP 405-201-00014

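### No weight, waist or BMI is scheduled at Visit 2 or Visit 3, so the SAP's double-blind baseline for them is a screening value taken 8 to 35 days before dosing

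*SAP*

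**What the plan says.** SAP 9.5.1 describes an ANCOVA of the "mean change from baseline of the double-blind treatment period to Day 42 (OC) and last visit" in body weight, with the same baseline weight as covariate. It also plans a CMH test of the proportions gaining or losing at least 7% from that baseline. Tables CT-13.1.1, CT-13.2 and CT-13.3 carry the double-blind baseline in their titles, and CT-13.1.2 places the 7% gains and losses in the double-blind period. SAP 7.1 defines that baseline as the last value available before the first double-blind dose.

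Protocol 3.7.5.3.1 puts the measurements in the physical examination: "height (screening only), weight, waist circumference, and calculation of body mass index (BMI) (screening and Day 42/ET only". It adds: "A complete physical examination will be performed at screening, and a targeted physical examination to address any new concerns" at the other marked visits. The physical examination row of Table 3.7-1 is marked at screening, Day 21 and Day 42/ET, and blank at Visit 2 (Day -7) and Visit 3 (Day -1).

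Vital signs are taken at Visits 2 and 3, and 3.7.5.3.2 gives their content: "Vital signs including systolic blood pressure and diastolic blood pressure, heart rate, respiratory rate, and body temperature". Weight is not in that list. It does appear among the vital-sign relevance criteria in Protocol Appendix 3 and SAP Appendix 1, as a 7% change from baseline.

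**The concern.** The SAP distinguishes a run-in baseline from a double-blind baseline, but for weight the schedule supplies one number that has to serve as both. SAP 7.2 already uses it as the run-in baseline in the demographic table. The interval between that number and first dosing is not inert. Table 4.1-1 requires subjects to stop stimulants, nonstimulants, antidepressants and weight-loss supplements before the run-in if they are taking them, and a week of placebo follows.

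Weight is a real safety question here. Protocol 1.3 lists among the most common adverse events "metabolism/nutrition-related (decreased appetite"). The 7% criterion is a threshold within each subject, so a displaced starting weight can move a subject across it in either direction. A reader of CT-13.1.1 or CT-13.1.2 would take the figures as change since randomization, and as scheduled they are not.

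**Working it through.** **Which scheduled weight comes last before dosing.** The parenthesis in 3.7.5.3.1 may limit all three measures, or BMI alone, to screening and Day 42/ET. On either reading the examination is not scheduled at Visit 2 or Visit 3, so the last scheduled weight before the first double-blind dose is the screening one. Two other passages support keeping weight apart from vital signs: the opening of SAP section 9 and Protocol 7.5.3 each name body weight separately from them.

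**The screening window.** The synopsis gives up to 28 days of screening plus a 1-week run-in: 28 + 7 = 35 days. This reproduces the Day -35 in Protocol 3.7.1.1, which places screening between Day -35 and Day -8.

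**Day counts.** Visit 3 is Day -1 and dosing starts the following day, Day 1, so there is no Day 0. Elapsed days from Day -a to Day b are a + b - 1.

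| From | To Day 1 | To Day 42 |
|---|---|---|
| Day -35 | 35 + 1 - 1 = 35 | 35 + 42 - 1 = 76 |
| Day -8 | 8 + 1 - 1 = 8 | 8 + 42 - 1 = 49 |
| Day -1 (Visit 3) | 1 + 1 - 1 = 1 | 1 + 42 - 1 = 42 |

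The part before Visit 3 is 76 - 42 = 34 days at most (34/76 = 45%) and 49 - 42 = 7 days at least (7/49 = 14%). Counting to Day 1 instead gives 35/76 = 46% and 8/49 = 16%, which changes nothing of substance.

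**What the analysed change contains.** Write the change from screening to Day 42 as P + T, where P is the change from screening to Visit 3 and T the change from Visit 3 to Day 42. Randomization takes place at Visit 3, after P has occurred, so the expected P is the same in every arm. It cancels from the expected difference between arms. It does not cancel from the change reported within an arm, and its variability is added to T.

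**The 7% threshold (illustration; both the 80 kg and the size of the shift are assumptions).** A screening weight of 80 kg puts the loss threshold at 80 × 0.93 = 74.4 kg. The loss since Visit 3 needed to be flagged is then:

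- weight at Visit 3 of 81 kg: (81 - 74.4)/81 = 8.1%
- weight at Visit 3 of 82 kg: (82 - 74.4)/82 = 9.3%
- weight at Visit 3 of 79 kg: (79 - 74.4)/79 = 5.8%

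The documents give no figure for the size, direction or frequency of such shifts.

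**The case against.** The strongest reply is that the trial's comparison is randomized. The ANCOVA and the CMH test compare arms, the screening weight precedes randomization in all of them, and washout and run-in effects balance in expectation. That stands. A reader might infer that the weight difference between drug and placebo is biased, and the documents do not support that. What the reply does not rescue is the within-arm change and the 7% rates, which count from the older weight in every arm.

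SAP 7.1 also makes the analysis computable and pre-specified: an old value under a stated rule is not a missing one. This stands too, and the problem is what the result is taken to mean.

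A reader might further infer that every screening weight was taken before washout. That is not established. Protocol 3.7.1.1 allows screening to take more than one visit, nothing fixes the examination at the first contact, and washout concerns only subjects on prohibited medication, whose proportion is not given.

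Nor does the SAP label the change itself as on-treatment. The phrase in SAP Appendix 1, "an on-treatment value must meet the" criterion, describes the later measurement and is accurate for Day 42.

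Finally, the vital-sign list in 3.7.5.3.2 is introduced as inclusive rather than exhaustive, and that section refers to Appendix 3, which lists weight. A site could therefore weigh subjects with the vital signs at Visit 3, and unscheduled weights are possible. The schedule does not plan either, and the cross-reference is itself a reason to state where weight is measured.

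**Conclusion.** The point holds as a mismatch between schedule and analysis. As scheduled, the double-blind baseline for weight, waist and BMI is a screening value 8 to 35 days old at Day 1, and 14% to 45% of the interval to Day 42 lies before the baseline visit. The within-arm changes and the 7% gain and loss rates therefore include weight change from before treatment and carry extra noise. The expected difference between arms is not biased.

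This rests on reading 3.7.5.3.2 as not including weight and on screening ending by Day -8. The 45% is the extreme of the window. The kilogram effect and the number of subjects reclassified cannot be obtained from the documents. An older weight may also be a weaker covariate, but nothing in the documents allows that loss to be quantified, so it carries no weight here. This is a worthwhile, inexpensive improvement to a safety analysis and does not touch the confirmatory results.

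**What to change.** Add weight and waist, with BMI calculated from screening height, to the Visit 3 (Day -1) column of Table 3.7-1 and to Protocol 3.7.5.3.1. Name that value as the double-blind baseline in SAP 9.5.1 and for the weight line of SAP Appendix 1. The cost is one extra weighing and waist measurement at a visit where vital signs are already taken, and about one line in each place.

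Where no Visit 3 weight is collected, title all CT-13 tables and the 7% rates as change from screening, and do not interpret them as change during double-blind treatment. This needs no new data. It is the option left for subjects already treated, since the SAP file carries statistical output run on 31 August 2020. Do not mix screening and Visit 3 baselines in one analysis.
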